### **E.3.2 Exclusion Criteria**

- Pregnant and lactating women, or planned pregnancy over the next 3 months
- Consumption of more than 14 (men) or 7 (women) alcoholic drinks per week
- History of disordered eating or eating disorder
- Body mass index (BMI) considered underweight (<18.5)
- Weight loss from metastatic cancer
- Unable to make dietary changes or participate in a 9-integrative medicine nutritional intervention
- Those with significant dietary changes, new medications, or new exercise routines within the past 90 days
- Currently, or already, a patient of [name] and Healthy Living Community

### **E.4 Participant and Procedure Schedule**

#### **E.4.1 Overview**

The study is comprised of 1 in-person screening, 2 follow-up visits, and 2 telephone or email check-in correspondences for additional support. The in-person screening and 2 virtual follow-up visits will take place at the Healthy Living Community clinic. Virtual follow-up study visits will take place via the Zoom video platform utilized by ChARM TeleHealth, a web-based and HIPAA compliant server maintained by the Healthy Living Community clinic and will occur at 5- and 9-weeks post-enrollment.

During the in-office screening, participants will have their joint mobility measured in accordance with the Brighton Scoring System to confirm that they meet the diagnostic criteria for Hypermobility Spectrum Disorder. Participants who are diagnosed using the Brighton criteria and meet other eligibility criteria will then be asked to provide informed consent (E.4.3) and enrolled in the study if willing. The Clinical Investigator will capture a complete and detailed medical history of enrolled participants, discuss family and social support, as well as prescribe a food plan. The CI will also assess the patient's current self-management strategies and provide general behavioral and psychosocial support. During the 2 follow-up visits, the Clinical Investigator will revisit these self-management strategies. As scheduling visits may be difficult at precisely 5 and 9 weeks, we will leave some flexibility for these points in time to accommodate the schedules of the Clinical investigator, the student researcher, and the participants.

At 2 and 6 weeks, the participants will be contacted by the student researcher to answer any questions, provide nutritional and psychosocial support, monitor for any adverse events, and offer solutions to any dietary challenges. Participants will also be assessed at all study visits for any adverse events.

Participants will be asked to complete pain (VAS), and health-related quality of life (PROMIS-29) instruments at baseline, 5, and 9 weeks. Adherence to the dietary recommendations, as well as the feasibility of food tracking will be obtained using *MyFitnessPal*, a food tracker app throughout the 9 weeks. A food plan satisfaction survey will be collected at 5 and 9 weeks. Participants will fill out the

#### **Protocol**

Study Title: Integrative Medicine for Hypermobility Spectrum Disorder (HSD) and Ehlers-Danlos (EDS) syndromes: A mixed-methods feasibility study (IMforHSDandEDS)

PI: [name]

IRB #: DH10320/PRAF

Approval Date: 03.03.21

Version: 3.0

patient assessment of care for chronic conditions (PACIC+) at baseline and the close-out visit during week 9.

#### **E.4.2 Telephone Screening**

Prospective participants will be contacted via telephone prior to their first visit. A standardized telephone script will be used to determine, as far as possible, if the participants meet the inclusion criteria and are eligible to join the study (See Appendix 3A).

In event that a prospective participant does not know if they have a Beighton score of 4 or more, a free screening will be required before scheduling the Screening visit. The medical assistant at Healthy Living Community clinic will confirm that prospective participants meet the eligibility requirements but will not record or capture any data. This will prevent prospective participants that are ineligible for the study from being scheduled for a screening visit. After the Beighton score is visually confirmed, the prospective participant will have the option to re-screen by telephone for the study and then be scheduled for a Screening Visit with the Clinical Investigator, if eligible.

If a participant meets all other criteria but is unable to attend the baseline visit in person, then they will be informed that they may attend the visit virtually, as long as they can provide medical documentation of a Beighton score of at least 4.

#### **E.4.3 Informed Consent**

Informed consent paperwork will be sent to the participant before their first visit so that they can review the document, but they will not sign anything until the first study visit. The study participants will meet with the student researcher to answer questions and to look over the consent forms prior to signing the document. The signed informed consent paperwork will be captured electronically via REDCap, a secure and HIPAA compliant web-based application used to capture electronic data for research studies (See Appendix 2B).

#### **E.4.4 Visit # 1: Screening (baseline)**

During the in-person screening visit, CDC Coronavirus Disease 2019 (COVID-19) doctor visit regulations will be followed, and all participants, the student researcher, and the Clinical Investigator will be required to wear facial masks, maintain a physical distance at 6 feet apart, and wash hands after all contact.

Participants will review the informed consent form with the student researcher, who will answer any questions. A signed form will be collected prior to initiating study-related activities. The Clinical Investigator (CI) will take range of motion measurements that will be obtained in accordance with The Beighton Scoring System to confirm that the participant meets the diagnostic criteria for Hypermobility Spectrum Disorder. BMI, height, and weight will also be collected. Participants will be screened for a history of disordered eating or eating disorders; if present; the participant will be referred to a specialized physician for treatment and excluded from the study. Participants with a body mass index (BMI) considered to be underweight, or less than 18.5, will also be excluded from the study. The CI will

#### **Protocol**

Study Title: Integrative Medicine for Hypermobility Spectrum Disorder (HSD) and Ehlers-Danlos (EDS) syndromes: A mixed-methods feasibility study (IMforHSDandEDS)

PI: [name]

IRB #: DH10320/PRAF

Approval Date: 03.03.21

Version: 3.0

calculate the daily caloric needs for each patient using the estimated energy requirements (EER) formula for each patient that takes into consideration their current physical activity level (i.e. sedentary or active), weight, and age. The CI will request consent to obtain the medical records of the participant.

The Clinical Investigator will do a thorough review of the patient's full medical history and listen to their entire background. They will discuss the social and familial support of the patient, assess their general diet, provide psychosocial support, and prescribe an anti-inflammatory food plan. The Clinical Investigator will also assess the patient's current self-management strategies and provide general behavioral and psychosocial support. Any current medications or supplements being used for pain that the participant is taking will also be documented, but no changes in medications will be required by the study. Participants will be given portal access to their electronic health records through ChARM Patient Portal for the use only of this study.

The student researcher will assist participants with logging into REDCap and collecting baseline pain (VAS), health-related quality of life (PROMIS-29) and patient assessment of care for chronic conditions (PACIC+) surveys. A baseline adverse events questionnaire will be obtained using the NUNM standardized multi-system survey for each participant, to document any current health conditions that may not be listed in the medical record. Participant demographic information will be collected, including age, sex, and gender

The student researcher will provide flyers with advice and guidelines for following a meal plan that follows an anti-inflammatory eating pattern, including recommendations for meal planning and strategies for adding and reducing certain foods (See Appendices Gi through Giv). The macronutrient breakdown that will be recommended for the patients will be 40- 50 % carbohydrate, 15- 20 % protein, and 35- 40 % fat, which is aligned with the Mediterranean-style eating pattern and has been shown to be anti-inflammatory. Participants will be provided a food plan that is in accordance with their current average dietary consumption of either 1800 or 2200 calories. (See Appendices 2Gi through 2Giv) Participants will also be given a list of resources for online and local Mediterranean-style eating patterns to simplify their research options. (See Appendix 2Gvi)

The student researcher will assist participants with downloading *MyFitnessPal* so that their estimated daily dietary intake can be captured. Participants will be assigned a *MyFitnessPal* username using an unidentifiable study number that will be recorded by the student researcher in a secure location, and the account will only be used for study purposes. Participants will be instructed that no identifiable health data related to the study will be shared on the *MyFitnessPal* app. The student researcher will also review the Sharing & Privacy settings in the *MyFitnessPal* app with participants to ensure that the privacy is protected as much as possible.

They will also provide a handout for how to use the app or website (See Appendix 2Gv). Participants will be given an opportunity to practice using the app with support from the study coordinator. Participants will be encouraged to track their diet daily to the best of their ability and will be able to opt-out of tracking if they express concerns. Using the Friends feature on the app, participants will be able to share

### **Protocol**

Study Title: Integrative Medicine for Hypermobility Spectrum Disorder (HSD) and Ehlers-Danlos (EDS) syndromes: A mixed-methods feasibility study (IMforHSDandEDS)

PI: [name]

IRB #: DH10320/PRAF

Approval Date: 03.03.21

Version: 3.0

their daily food tracking with the student researcher, and the data will be collected at 5 and 9 weeks. Participants will be given a 1-week lead-in period so that they can adjust to tracking their dietary intake before starting the food plan and will be instructed to contact the student researcher with any questions.

In the event that the baseline visit is conducted virtually, all procedures will be the same, except that the participant will provide medical documentation of a Beighton score of 4 or more, in lieu of a Beighton measurement being obtained at the visit. We will require informed consent prior to capturing this documentation. The participant will be asked to report their own height and weight. All other data will be captured electronically. Any participant who completes the baseline visit remotely will be invited to complete the Week 5 visit in person, if possible; if the Week 5 visit is completed in person, then weight, height, and Beighton score will be confirmed at that visit.

#### **E.4.4.1 Food Plan Satisfaction Survey**

We will distribute food plan satisfaction surveys via REDCap to be completed by the participant prior to the patient's next visit (5 weeks). The surveys will gather information regarding the overall cost-effectiveness and feasibility of the diet and any obstacles that are faced with the food plan. (See Appendix 2F)

#### **E.4.5 Check-in #1 (2 weeks)**

Participants will receive a phone call or e-mail from the student researcher that will answer any questions, provide nutritional and psychosocial support, and offer solutions to any dietary challenges. The goal is to provide support with dietary adherence. This will occur 2 weeks after Visit # 1 and will be set up in advance at a time that works for the participant. If the participant is not available, we will send a check-in email and answer any questions, provide nutritional and psychosocial support, and offer solutions to any dietary challenges by email, if requested. The nutrition counseling script contains suggestions for a general healthy eating pattern but is not a part of food plan adherence. (See Appendix 3B)

Participants will be assessed for any adverse events with the following question, "Are you experiencing any new symptoms or side-effects that you may have noticed?" (See Appendix 3B)

#### **E.4.6 Visit # 2: Follow-up (5 weeks)**

During the second virtual clinical visit, the student researcher will collect VAS pain measurements, health-related quality of life scores (PROMIS-29) and will assess for any adverse events using the NUNM standardized multi-system questionnaire.

The Clinical Investigator will discuss the social and familial support of the patient, provide psychosocial support, and address any concerns with the anti-inflammatory food plan. The CI will also assess the patient's current self-management strategies and provide suggestions for any adjustments to general behavioral and psychosocial support recommendations. Any current medications or supplements being

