#### **E.4.8 Visit # 3: Follow-up (9 weeks)**

During the final virtual visit, the student researcher will collect VAS pain measurements, patient assessment of care for chronic conditions (PACIC+), PROMIS-29 health-related quality of life scores and will assess participants for any adverse events using the NUNM standardized multi-system questionnaire.

The Clinical Investigator will discuss the social and familial support of the patient, provide psychosocial support, and address any concerns with the anti-inflammatory food plan. The CI will also assess the patient's current self-management strategies and provide suggestions for any adjustments to general behavioral and psychosocial support recommendations. Any current medications or supplements being used for pain that the participant is taking will also be documented, but no changes in medications will be required by the study. Current self-reported weight will also be documented.

At the final visit, patients will be encouraged to continue to eat a healthy diet but will be reminded that the study is complete and that they may alter their diet in whatever way they wish.

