#### Providing psychosocial support

Psychosocial support will be provided by both the Clinical Investigator, the student researcher, and *MyFitnessPal* throughout the 9-week program. Participants will receive behavioral, lifestyle, and dietary counseling all through a total of 3 office visits with the medical doctor, and 2 phone calls or e-mail check-in correspondences with the student researcher.

The student researcher has personal experience with both hEDS and Postural Tachycardia Syndrome (POTS), and similar to another EDS study, this will be disclosed to participants at the beginning of the interview in an effort to mitigate the power imbalance that often accompanies research. This may also help “instill greater confidence in participants” to share their experiences with a researcher and EDS individual who is also in their “in-group.” It will also be “emphasized that it [is] their stories that matter” for the purpose of the study.

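### Pain, quality-of-life and care-rating outcomes are collected at the follow-up visits by the student researcher who also delivers support, with no provision for completing them away from that person

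*Combined protocol and SAP*

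**What the plan says.** **Who collects, and when.** At week 5 (E.4.6), during the virtual visit, "the student researcher will collect VAS pain measurements, health-related quality of life scores (PROMIS-29"). At week 9 (E.4.8), "the student researcher will collect VAS pain measurements, patient assessment of care for chronic conditions (PACIC+), PROMIS-29 health-related quality of life scores".

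**What else that person does.** E.4.5 describes the first check-in: "Participants will receive a phone call or e-mail from the student researcher that will answer any questions, provide nutritional and psychosocial support". E.4.7 repeats this for the second. E.5 places the student researcher in the provider team and states: "Psychosocial support will be provided by both the Clinical Investigator, the student researcher". The same section says "The student researcher has personal experience with both hEDS and Postural Tachycardia Syndrome (POTS") and that "this will be disclosed to participants at the beginning of the interview".

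**How the instruments are completed.** E.4.1 describes VAS, PROMIS-29 and PACIC+ as completed by participants. At baseline (E.4.4) the student helps participants log into REDCap for all three. E.7.1 names REDCap as the place where they are recorded. For weeks 5 and 9 the plan does not say whether the participant enters the answers alone, enters them with the student present, or gives them to the student.

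**The comparison within the plan.** For the food plan survey, E.4.4.1 says: "We will distribute food plan satisfaction surveys via REDCap to be completed by the participant prior to" the next visit. E.4.6.1 does the same for week 9.

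**Analysis.** E.9 tests whether the intervention reduced pain and improved quality of life, using paired t-tests or Wilcoxon signed-rank tests. PACIC+ also has a paired t-test from baseline to study end.

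**The concern.** All three instruments are subjective, and participants know what they are receiving. The person collecting them at follow-up has by then also been giving support. PACIC+ is the most exposed: it rates the experience of care, and at week 9 it is collected by someone who has been giving part of that care.

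Participants may soften their answers out of courtesy to someone who has helped them. If that tendency is stronger at weeks 5 and 9 than at baseline, it goes straight into the change score. The likely direction is towards improvement. There is no control arm in which the same tendency could be seen, so neither a paired t-test nor a signed-rank test can separate it from an intervention effect. What is at stake is how the pain, quality-of-life and PACIC+ changes are read, including any use of them to plan the larger study that section F has in view.

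**Working it through.** **1. Setting the sections side by side.** The plan states no power, alpha or SD for these outcomes, so there is no figure of its own to reproduce. The main check is textual.

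| Question | Baseline | Week 5 | Week 9 |
|---|---|---|---|
| Instruments | VAS, PROMIS-29, PACIC+ | VAS, PROMIS-29 | VAS, PROMIS-29, PACIC+ |
| Role of the student | Helps with REDCap login and collection (E.4.4) | Collects during the visit (E.4.6) | Collects during the visit (E.4.8) |
| Support check-ins by the student beforehand | None | One (E.4.5) | Two (E.4.5, E.4.7) |
| Completion away from the student specified? | No | No | No |
| Food plan survey | Not described in E.4.4 | By REDCap before the visit (E.4.4.1) | By REDCap before the visit (E.4.6.1) |

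Two things follow. First, the collector also delivers part of the intervention, and the planned support contact accumulates between the assessments being compared. Second, unattended REDCap completion before the visit is already set up for one survey at the same two time points, and REDCap already holds the three instruments at issue.

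**2. What a shift would do to the test (illustration only).** Inputs from the documents: 20 participants and a 75% retention goal (B.1), giving 0.75 × 20 = 15 completers at the goal. Inputs assumed, because the documents give none: two-sided alpha 0.05; SD of VAS change s = 2, range 1.5 to 2.5; true change zero; courtesy shift b of 0.25, 0.5 or 1.0 points.

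The paired t statistic then follows a noncentral t distribution with n − 1 degrees of freedom and noncentrality (b/s) × √n. The rejection rate is the probability that |t| exceeds the critical value, which is 2.145 for n = 15 and 2.093 for n = 20.

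- n = 15, b = 0.5, s = 2: noncentrality 0.25 × 3.873 = 0.968; rejection rate 0.147.
- n = 20, b = 0.5, s = 2: noncentrality 0.25 × 4.472 = 1.118; rejection rate 0.186.

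| Shift (points) | SD of change | n = 15 | n = 20 |
|---|---|---|---|
| 0 | any | 5% | 5% |
| 0.25 | 2 | 7% | 8% |
| 0.5 | 2 | 15% | 19% |
| 0.5 | 2.5 to 1.5 | 11% to 23% | 14% to 29% |
| 1.0 | 2 | 44% | 56% |
| 1.0 | 2.5 to 1.5 | 30% to 67% | 40% to 81% |

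At a 0.5-point shift with SD 2, nearly all rejections point to reduced pain (0.145 of 0.147, and 0.185 of 0.186). The table shows how exposed the test is to a shift of a given size. It does not estimate the shift.

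**The case against.** **The plan already has participants completing these forms in REDCap.** This stands. A reader might infer from E.4.6 and E.4.8 that answers are spoken to the student, or that self-completion in REDCap is kept for the satisfaction survey. E.4.1, E.4.4 and E.7.1 do not support either reading. What remains is narrower: the visit text ties collection to a visit and to an intervention provider, allows answers to be given to that person, and nowhere provides for private completion.

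**Growing rapport is assumed.** This stands in part. Disclosure of the shared diagnosis comes at the start of the interview and may affect every time point, and the two check-ins may be by email. The differential risk therefore rests mainly on the support relationship, and how strong that becomes is unknown.

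**PACIC+ looks back six months** (E.6). At week 9 about 9 of 26 weeks (35%) fall within the study, so much of the recall period predates this team. That weakens the PACIC+ argument but does not remove it, because the person collecting the form still gave part of the recent care.

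**The magnitude is assumed, and self-completion would not remove all reporting bias.** Both points are correct. Participants would remain unblinded in a single arm. The change removes one avoidable source only.

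**Moving surveys before the visit could disturb retention.** This is a fair point. B.1 and E.6 count completed visits, whereas E.9 counts participants from whom follow-up data are obtained. Someone who returns a survey and then misses the visit would be counted differently. The fix has to close that gap.

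A reader might also want participants to be told that the care team will not see their answers until the study ends. The documents do not allow that promise: a baseline VAS of 1 or more is an enrolment criterion (E.3), and the study team has access to REDCap (E.7.1).

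**Conclusion.** The point holds as a design weakness that should be corrected. At weeks 5 and 9 an intervention provider collects subjective outcomes at the visit, no private completion is specified, and a less exposed route is already in use in the same study. With paired pre-post tests and no control arm, any reporting shift that grows between baseline and follow-up would be read as change.

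The size is not known from the documents. The figures of 15% and 19% depend on an assumed 0.5-point shift, an assumed SD of change of 2, a two-sided alpha of 0.05 and no true change.

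A reader might infer that biased collection has been shown, or that the study's main conclusion is threatened. Neither follows. Courtesy reporting is a plausible risk that the documents neither state nor measure. Pain and quality of life are tertiary and PACIC+ is exploratory, so the primary outcomes of recruitment and retention are unaffected by it.

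**What to change.** - **E.4.6 and E.4.8:** state that VAS, PROMIS-29 and (week 9) PACIC+ are self-completed by the participant through a REDCap link before the visit, as for the food plan satisfaction survey, and that the student researcher gives technical login help only.
- **E.4.4:** state that the participant enters the baseline answers directly in REDCap, with staff still seeing the baseline VAS for eligibility.
- **B.1, E.6 and E.9:** state that a pre-visit survey alone does not count as a completed visit for retention.
- **Adverse-event questions** stay with staff.
- **No assurance** should be given that the care team will not see the answers.

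The cost is REDCap survey settings and short edits to these sections. Treatment and sample size do not change. The downside is a few late or incomplete surveys. Automatic reminders, or completion at the visit as a fallback, would deal with most of these, and the mode of completion should be recorded so that it can be reported with the results.
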